### 3.2.3. Days in Hospital for Heart Failure

The objective is to demonstrate that treatment with the BAROSTIM NEO System, relative to medical management, decreases the number of days in the hospital for heart failure. Analysis will be based on a similar negative binomial model as the primary endpoint, including the definition of follow-up time and the same negative binomial regression model for estimation and producing a nominal two-sided 95% confidence interval and p-value for the treatment effect. Similar to the primary endpoint, to further incorporate the impact of the timing that the events occur over follow-up, alternative methods of analysis will be performed as described in Section 5.3.

**Rationale:** Days in the hospital for heart failure represents a patient-relevant outcome that measures the severity of their heart failure as measured by hospitalization days. The endpoint accounts not just for the number of heart failure hospitalizations, but also the length or severity of those hospitalizations. The days in hospital for heart failure can provide relevant information for patient and physician decision-making.

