#### 3.1.4. Analysis Method

The hypothesis test will be based on a Z-statistic for the estimate of  $\beta_1$  from a negative binomial regression model. Although randomization is expected to result in balanced baseline covariates between the two arms, the model will include the baseline covariate of number of heart failure hospitalizations 12 months prior to enrollment to adjust for any potential imbalances between the two arms. In SAS (version 9.4 code) this model is fit as follows:

```
proc genmod;  
  model nev=trt hfh / dist=negbin offset=lfutime;  
run;
```

where nev is the number of events, trt is an indicator variable of randomization to the treatment arm, hfh is the number of heart failure hospitalizations within the 12 months prior to enrollment, and lfutime is the logarithm of the follow-up time. The Z-statistic (Z) is the parameter estimate for trt divided by the associated standard error. A Wald test one-sided nominal p-value is calculated by calculating the standard normal tail probability  $\Phi(Z)$ . This simplified model has previously been demonstrated to provide treatment effect estimates in strict agreement with those obtained with the more complex joint model defined in the BADR.

Success for demonstrating a reduction in morbidity and mortality is determined by the z-statistic crossing the group sequential boundary at one of the pre-specified analyses whose timing is determined by reaching pre-specified numbers of events.

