## 5.3. Alternative Statistical Methods for Analyzing Rates

To further incorporate the impact of the timing that the events occur over follow-up, alternative methods of analysis on the endpoints will be performed. These will include, at a minimum, the Anderson Gill method for recurrent events, and semi-parametric joint frailty models (JFM).

The JFM analysis is intended to aid the interpretation of the primary negative binomial model analysis by providing insight into the contribution of censoring events and recurrent heart failure hospitalization events to the overall (marginal) treatment effect estimated by the negative binomial model analysis. This JFM has a demonstrated ability to provide unbiased estimate of the treatment effect on recurrent heart-failure hospitalizations in the presence of dependent censoring (i.e., censoring being more likely in subjects at higher risk of heart-failure hospitalization). In the JFM, the dependence of censoring and recurrent events is accounted for by a frailty term, which measures a patient-specific tendency to have an increased likelihood of both types of events. The model assumes that a patient's censoring and recurrent events are independent of each other after conditioning on the frailty term. The JFM will be implemented using piecewise constant hazards for the recurrent events and censoring events. This method may be implemented by Gaussian quadrature using SAS PROC NLMIXED24. Piecewise constant hazard time intervals will be defined prior to performing analyses comparing treatment arms. For each hazard ratio comparing the two arms, a 95% confidence interval and p-value will be calculated using the Wald method. The JFM analysis will be repeated with only death as a dependent censoring event and transplant/LVAD as non-informative censoring events.

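### The nominal 95% interval and p-value for heart failure hospital days are not assured their stated coverage, because summed stays are analysed with the primary's model-based negative binomial standard error

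*SAP*

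**What the plan says.** Days in hospital for heart failure is one of the focused endpoints in SAP 3.2. Section 3.2.3 carries the primary model over: "Analysis will be based on a similar negative binomial model as the primary endpoint". The same sentence specifies "the same negative binomial regression model for estimation and producing a nominal two-sided 95% confidence interval and p-value for the treatment effect".

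SAP 3.1.4 gives the model as "model nev=trt hfh / dist=negbin offset=lfutime", fitted in PROC GENMOD with no REPEATED statement. The test is defined there too: "The Z-statistic (Z) is the parameter estimate for trt divided by the associated standard error". That is a model-based Wald standard error.

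The rationale in 3.2.3 describes the outcome: "The endpoint accounts not just for the number of heart failure hospitalizations, but also the length or severity of those hospitalizations". Each admission therefore adds its whole length. Section 3.2.3 also says that "alternative methods of analysis will be performed as described in Section 5.3"; that section names Andersen-Gill and joint frailty models to reflect event timing. Neither document gives a robust variance, a bootstrap or a two-part model for days.

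Under SAP 3.2 the focused endpoints are reported with nominal intervals and p-values and no multiplicity adjustment, and are meant to support labeling.

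**The concern.** A negative binomial model has one dispersion parameter. For event counts that is enough. For days, the same parameter must describe both the share of subjects with no days at all and the spread of stay lengths among those admitted. The two need not agree, and the model-based standard error follows whatever value the likelihood settles on. If the spread of stays is small, the standard error can be too large and a real benefit may be missed. If stays are skewed, or if admissions ending in death, assist device or transplant add days over a short follow-up, it can be too small and a chance difference may look like a benefit. Since no multiplicity adjustment is made, readers will take this interval at face value.

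**Working it through.** **1. Reading the dispersion, checked against the plan's own figure.** SAP Table 2 states that a 28% observed reduction is the minimum for success on the primary. Inputs: 331 subjects 1:1 (n = 165.5 per arm), 320 events, final boundary 2.4335 (SAP Table 7), and dispersion 1.7 (SAP 8.1) read as a gamma shape, because the large-overdispersion scenario uses the smaller value 1.4.

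Var(log ratio) = (1/n)(1/μc + 1/μt + 2/1.7)

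The mean events per subject sum to 320/165.5 = 1.934. At the solution μc = 1.131 and μt = 0.802, so SE = 0.1414 and the minimum reduction is 1 − exp(−2.4335 × 0.1414) = 29.1% (29.3% with 319 subjects). That is close to 28%. Reading 1.7 as a variance multiplier (2 × 1.7 in place of 2/1.7) gives SE 0.1835 and 36%. The shape reading fits.

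**2. Event counts.** In simulated null trials with 319 subjects, the model SE averaged 0.141, the true SD of the log ratio was 0.141 and two-sided error was 5.5%. The model is sound for the primary outcome.

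**3. Days: why the SE goes wrong.** Assumptions not in the documents: 0.28 admissions per year (70% of the 0.4 event rate), lognormal stays with mean 6 days and log-SD s, and follow-up uniform from 1 to 4.8 years (mean 2.9). Protocol 4.3.3 expects 2.3 years, but 320 events among 331 subjects at an average rate of (0.4 + 0.26)/2 = 0.33 need 320/(331 × 0.33) = 2.9 years. Mean admissions per subject are m = 0.28 × 2.9 = 0.812. With equal follow-up and no covariate, n = 159.5 per arm and c² = exp(s²) − 1:

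- true variance = (2/n)[(1 + c²)/m + 1/1.7]
- model variance = (2/n)[1/(6m) + k], where k is the fitted dispersion
- k needed for the two to agree = (1 + c²)/m + 1/1.7 − 1/(6m)
- k implied by a simulated model SE = SE² × n/2 − 1/(6m), with 1/(6m) = 0.205

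The simulated columns come from 600 null trials per row. Error is two-sided, with 5% intended.

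| s | True SD, formula | True SD, simulated | Model SE, simulated | k needed | k implied | Error, model SE | Error, sandwich |
|---|---|---|---|---|---|---|---|
| 0.5 | 0.165 | 0.184 | 0.229 | 2.0 | 4.0 | 1.3% | 6.2% |
| 0.8 | 0.191 | 0.214 | 0.236 | 2.7 | 4.2 | 3.0% | 6.2% |
| 1.1 | 0.243 | 0.253 | 0.245 | 4.5 | 4.6 | 5.5% | 5.8% |
| 1.4 | 0.342 | 0.341 | 0.255 | 9.1 | 5.0 | 16.3% | 9.7% |

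The true SD nearly doubles down the table while the model SE rises by about a tenth. The share of subjects with no admission is (1 + 0.812/1.7)^(−1.7) = 51%, whatever the stay length, and the k that reproduces this share of zeros is 4.8. The implied values stay near it, while the k required moves from 2.0 to 9.1. The two agree only near s = 1.1.

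**4. Other assumptions.** Null trials, 500 to 600 per setting, event rate 0.4, 18% of events terminal (SAP 8.1) and 75% of events assumed to be admissions:

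| Stay (mean, SD in days) | Days from terminal admissions | Model SE ÷ true SD | Error, model SE |
|---|---|---|---|
| 18, 9 | no | 1.48 | 0.2% |
| 5, fixed | no | 0.248/0.187 = 1.33 | 1.5% |
| 6, 6 | no | 1.03 | 4.2% |
| 6, 6 | yes | 0.265/0.306 = 0.87 | 9.5% |
| 7, 12 | yes | 0.277/0.361 = 0.77 | 13.0% |

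Over all settings of this kind, including a true ratio of 0.65, the model SE was 0.74 to 1.48 times the true SD, with non-coverage from 0.2% to 13.0%. The sandwich SE was 0.87 to 1.03 times the true SD, with non-coverage from 3.8% to 11.2%. A further set (mean stay 6 days, same event rate and terminal share) gave model-SE error of 2.3% to 17.2% without terminal days and 13.7% to 29.3% with them; sandwich error was 5.7% to 14%. At 600 trials the Monte Carlo standard error at 5% is √(0.05 × 0.95/600) = 0.9 percentage points.

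**5. Point estimate.** At a true ratio of 0.65, the geometric mean of the estimated ratios for days lay between 0.618 and 0.659. The main problem is the interval, not the estimate.

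**6. What the documents show about spread.** Protocol Table 4 reports the pre/post change in hospital days with SE 4.0 (N = 38) in the device arm and 2.2 (N = 34) in the control arm. These imply SDs of 4.0 × √38 = 24.7 and 2.2 × √34 = 12.8 days. Days vary widely between subjects, but this is a change per subject, not a length per stay, and it does not settle the direction.

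**The case against.** The endpoint is nominal, has no success rule and cannot alter the primary result. Part of the plausible range is conservative: with fairly uniform stays the interval is too wide, which costs power but creates no false claim. In some settings coverage is right. Section 5.3 promises further methods, and the size of the problem rests on lengths of stay that no one has stated.

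Most of this stands and limits the point. It does not remove it. Waiving multiplicity adjustment does not waive the coverage of each 95% interval, and SAP 3.2 ties these analyses to labeling. The Section 5.3 methods address when events occur; they are not set out for a sum of days, and no robust variance is stated for them. The word similar in 3.2.3 might seem to leave the variance open, but the same sentence goes on to specify the same regression for the interval and p-value.

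Three stronger readings are tempting and unsupported:

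- **That the interval is certainly wrong, or certainly too narrow.** The sign depends on stay length and on days from terminal admissions, and the documents settle neither.
- **That the primary shares the fault.** For event counts the model SE matched the true SD (step 2).
- **That a sandwich variance is a complete cure.** It left up to 14% error in the harshest settings.

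**Conclusion.** The concern holds as a matter of assurance: nothing in the plan makes the nominal 95% interval and p-value for hospital days reliable. Across the assumed ranges, two-sided error runs from about 1% to well above 10%, and it is near 5% only where an over-wide and an over-narrow tendency cancel. These figures rest on assumed lognormal or fixed stays, the assumed share of events that are admissions, follow-up of 1 to 4.8 years, and the handling of terminal admissions. The mechanism does not depend on the particular values. The consequence is confined to one focused endpoint that supports labeling. It is worth correcting because the correction is cheap.

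**What to change.** In SAP 3.2.3, keep the negative binomial rate ratio with its covariate and follow-up offset, but take the 95% interval and p-value from a subject-level empirical (sandwich) variance. Pre-specify a subject-level bootstrap interval or a permutation p-value alongside it, because the sandwich reduces the miscoverage without removing it under very skewed stays. The SAP already uses the bootstrap for the win ratios and for clinical stability, so it is not a new tool for this plan. Neither the bootstrap nor the permutation test was tried in the simulations above, so their performance here is not shown. The same sentence should state whether days from an admission that ends in a terminal event are counted, since this moved the error as much as the spread of stays did.

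The cost is one program option, one SAP sentence and an interval that may turn out wider. The change should be fixed before hospital days are compared between arms.

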### 3.2.4. Long Term Sustainable Improvement

#### Six Minute Hall Walk (6MHW)

The mean improvement in 6MHW between baseline and 12 months by treatment arm will be presented with means and confidence intervals using a regression model of change from baseline with covariates for randomized group and baseline value. A generalized estimating equation (GEE) repeated measures model with a compound symmetry working correlation will be used to account for within subject correlation over time and to estimate the difference between the randomized arms over all times at which the endpoint is collected, adjusted for baseline.

**Rationale:** Improving symptoms is important to patients, particularly an improvement in exercise capacity (6MHW). Previously, a clinically and statistically significant symptomatic improvement was established at six months for 6MHW. This endpoint will evaluate the long term, sustainability of an improvement in 6MHW between the treatment arms.

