### 3.2. Focused Endpoints

Based on discussions in November 2022 between the FDA and the BeAT-HF Steering Committee, as well as CVRx and an independent statistician, a set of focused and clinically relevant endpoints were pre-specified. The purpose of these pre-specified focused endpoints is to provide a structure to evaluate the totality of the data while limiting the potential for a type I error inflation among non-primary endpoints. The primary endpoint and analysis method remains unchanged, and the analysis of all focused endpoints will be performed independently from the results of the primary endpoint.

The pre-specified focused endpoints were identified prior to the unblinding of the data. These focused endpoints are a subset of the endpoints and analyses pre-specified in the Statistical Analysis Plan, with minor clinically justified and statistical clarifications. The analyses of the focused endpoints will be based on descriptive statistics, nominal two-sided 95% confidence intervals and p-values. No statistical adjustment for multiple comparisons will be made.

These analyses are intended to support any updated labeling for patients with heart failure.

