#### Minnesota Living With Heart Failure (MLWHF)

The mean improvement in MLWHF between baseline and 12 months by treatment arm will be presented with means and confidence intervals using a regression model of change from baseline with covariates for randomization group and baseline value. A generalized estimating equation (GEE) repeated measures model with a compound symmetry working correlation will be used to account for within

subject correlation over time and to estimate the difference between the randomized arms over 12 months of follow-up, adjusted for baseline.

**Rationale:** Improving symptoms is important to patients, particularly an improvement in Quality of Life. Previously, a clinically and statistically significant symptomatic improvement was established at six months for QOL. This endpoint will evaluate the long term, sustainability of an improvement in QoL between the treatment arms.

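### SAP 3.2.4 does not name the 12-month arm difference as its lead result, and the between-arm estimate it does specify pools months 6 and 12

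*SAP*

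**What the plan says.** For each of the three endpoints, SAP 3.2.4 describes two analyses.

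- **A 12-month regression.** For 6MHW its output is described as follows: "The mean improvement in 6MHW between baseline and 12 months by treatment arm will be presented with means and confidence intervals". The model regresses the change score on arm and the baseline measurement. MLWHF and NT-proBNP have the same structure, with NT-proBNP log transformed.
- **A repeated measures GEE with compound symmetry.** Only this model is given the task of comparing the arms. For 6MHW and NT-proBNP its purpose is "to estimate the difference between the randomized arms over all times at which the endpoint is collected, adjusted for baseline". For MLWHF it is "to estimate the difference between the randomized arms over 12 months of follow-up, adjusted for baseline". Neither a visit term nor an arm-by-visit term is mentioned.

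The rationale for 6MHW reads: "Previously, a clinically and statistically significant symptomatic improvement was established at six months for 6MHW". It goes on to give the aim of the endpoint: "This endpoint will evaluate the long term, sustainability of an improvement in 6MHW between the treatment arms". The other two endpoints have parallel rationales.

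Protocol 3.4.11.2 and 3.4.11.3 place follow-up 6MHW and NT-proBNP at months 6 and 12 only. Protocol 3.4.11.5 places MLWHF at months 6, 12, 18 and 24, so a 12-month horizon again leaves months 6 and 12.

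SAP 3.2 says that the focused endpoints are reported with descriptive statistics, nominal two-sided 95% intervals and p-values, without multiplicity adjustment, and that they are meant to support labelling.

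**The concern.** In this section the six-month effect is the premise and month 12 is the question. A single arm difference taken over both visits mixes the two. If the benefit had gone by month 12, a large six-month effect could still make the pooled difference nominally significant.

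The plan also leaves two candidate results for one question: the group term of the 12-month regression and the pooled GEE difference. It does not say which one leads, so the choice can be made after both are seen. SAP 3.2 gives limiting type I error inflation among the non-primary endpoints as a reason for the focused set, and an unnamed lead estimate works against that.

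Much of the six-month input was not new when the focused endpoints were set in November 2022. SAP Table 1 lists six-month 6MHW, quality of life and NT-proBNP data for the subgroup in submissions dated December 2018 and April 2019. The SAP also states: "The pre-specified focused endpoints were identified prior to the unblinding of the data". That may refer to the later data, so the two statements need not conflict, but the reader should be told which data had been seen.

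**Working it through.** The documents give no sample size, power or expected effect for these endpoints, so there is no planning figure to reproduce. The SD input was checked instead.

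**1. SD for 6MHW.** Protocol Table 3 (earlier randomized studies) gives standard errors of 14.1 (n = 56) and 13.2 (n = 43), and a difference of 58.1 with SE 19.8.
- Arm SDs: 14.1 × √56 = 105.5 and 13.2 × √43 = 86.6. The pooled SD is 97.8 m.
- Check: 97.8 × √(1/56 + 1/43) = 19.8, which matches the table.

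**2. Pooled estimate when the 12-month difference is zero.** Let d6 be the true six-month difference and ρ the within-subject correlation. With two visits, equal SDs, complete data and compound symmetry:
- estimate = d6 / 2
- SE = SD × √((1 + ρ)/2) × √(2/n), with n = 319/2 = 159.5 per arm. The 319 is from SAP section 1 and the 1:1 allocation from Protocol 3.1.
- At ρ = 0.5: 97.8 × 0.866 × 0.112 = 9.5 m. At ρ = 0.3 it is 8.8 m, and at ρ = 0.7 it is 10.1 m.

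Probability of two-sided p < 0.05 for the pooled difference:

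| d6 (m) | Pooled estimate (m) | ρ = 0.3 | ρ = 0.5 | ρ = 0.7 |
|---|---|---|---|---|
| 20 | 10.0 | 0.205 | 0.184 | 0.168 |
| 30 | 15.0 | 0.397 | 0.353 | 0.318 |
| 40 | 20.0 | 0.620 | 0.559 | 0.508 |
| 58.1 | 29.1 | 0.908 | 0.865 | 0.820 |
| 81.9 | 41.0 | 0.996 | 0.991 | 0.982 |

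The 58.1 m effect is from Protocol Table 3 and the 81.9 m effect from Table 4 (no CRT at baseline). The other effects and ρ are assumptions. With 240 subjects and 58.1 m, the range is 0.70 to 0.81. A test of the 12-month difference alone rejects at 0.05 by construction in every row.

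**3. In terms of observed z-values.** Pooled z = ((z6 + z12)/2) / √((1 + ρ)/2).
- z6 = 4, z12 = 0: z = 2.31 (p = 0.021) at ρ = 0.5 and 2.17 (p = 0.030) at ρ = 0.7.
- z6 = 4, z12 = 1 (p = 0.32 alone): p = 0.004 to 0.007.
- z6 = 58.1/19.8 = 2.93, z12 = 0: z = 1.69 and 1.59, p = 0.09 and 0.11.
- Break-even with z12 = 0: z6 = 2 × 1.96 × √((1 + ρ)/2), which is 3.39 at ρ = 0.5 and 3.61 at ρ = 0.7.

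**4. MLWHF.** With an SD of about 23 (Protocol Tables 3 and 4 give 22.6 and 22.9), the probability is 0.98 or more for a 19.5-point six-month effect and 0.56 to 0.67 for 10 points. NT-proBNP was not calculated, because the documents give no SD on the log scale.

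**5. Simulation check.** Exchangeable GEE with a visit term and robust SE, 318 subjects, ρ = 0.5, 150 runs per scenario.
- d6 = 58.1: mean estimate 28.5 m, rejection 0.85.
- The same with an assumed 25% missing at month 12: weight shifts to month 6, with estimate 34.4 m and rejection 0.95. SAP section 7 says that COVID-19 reduced or delayed such tests, but gives no number.
- d6 = 30: estimate 14.0 m, rejection 0.33.
- In these three scenarios the 12-month regression rejected in 3% to 8% of runs, and a 12-month contrast from an arm-by-visit GEE in 3% to 9%. The Monte Carlo error is about 2 points, so this is too coarse to confirm 5% closely. Scenarios with no effect at either visit were not completed.

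**The case against.** The strongest reply is that a 12-month comparison is already in the plan. The regression of 12-month change contains a group covariate, and its coefficient is the baseline-adjusted 12-month arm difference. Its means and intervals by arm would show a loss of effect. This stands. A reader might infer that the plan has no 12-month analysis, or that a vanished benefit would be hidden; the text supports neither. What is missing is the designation of that coefficient as the answer.

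A reader might also infer that sustainability could be declared with no 12-month benefit. SAP 3.2 and 3.2.4 contain no hypothesis, threshold or success rule for sustainability, so there is nothing to declare.

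Three further points stand in part.
- An arm difference averaged over visits is a legitimate quantity, and the SAP names it openly. It answers a different question from the one in the rationale.
- The absence of an arm-by-visit term is an inference from silence. This SAP supplements a main SAP that is not available here. All that can be said is that no such term is stated.
- The size depends on the six-month effect. With the earlier studies' own z of 2.93 the pooled p is not below 0.05, and a 20 m effect gives a probability of only about 0.2.

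Finally, not all six-month data had been seen. SAP section 1 reports 59 subjects randomized in the later period, ending in July 2020, and much of their six-month data would postdate the April 2019 submission.

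**Conclusion.** The point holds as a mismatch between question and named estimate. SAP 3.2.4 asks about durability beyond six months, assigns the between-arm difference only to a GEE that reads as pooled over months 6 and 12, and does not say whether that or the 12-month regression answers the question.

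For 6MHW with no 12-month difference, the pooled result reaches nominal significance with probability about 0.2 for a 20 m six-month effect, 0.3 to 0.4 for 30 m and 0.8 to 0.9 for 58 m. These figures are illustrative. The SD and the 58.1 m effect come from the earlier studies, not this trial's subgroup. The correlation is assumed, and the base case has complete data for 319 subjects.

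What is affected is the estimate and nominal p-value offered in support of labelling. The primary endpoint is untouched.

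**What to change.** For 6MHW, MLWHF and NT-proBNP, name the baseline-adjusted 12-month between-arm difference as the focused estimate, with its confidence interval and p-value. It can be the group term of the regression already planned, or a 12-month contrast from a GEE or MMRM with arm-by-visit terms; the SAP should say which. Report the pooled GEE difference as supportive. State that six-month data for most of the subgroup had been analysed earlier. By SAP section 1, up to 319 − 59 = 260 of 319 subjects (82%) were randomized before the later group, but the number actually analysed at six months is not given and should be added.

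The cost is SAP wording and at most one model term. Some precision is lost: the SE of the 12-month difference is 1/√((1 + ρ)/2) times that of the pooled one, so about 8% larger at ρ = 0.7, 15% at 0.5 and 24% at 0.3. No new data are needed.
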